6.2 Preparation, Handling, Storage, and Accountability

The investigator or authorized study site staff must confirm appropriate temperature conditions have been maintained during transit for all study intervention received, and any discrepancies are reported and resolved before use of the study intervention.

Only participants enrolled in the study may receive study intervention, and only authorized study site staff may supply or administer study intervention. All study intervention must be stored in a secure, environmentally controlled, and monitored (manual or automated) area in accordance with the labeled storage conditions with access limited to the investigator and authorized study site staff.

The investigator, site, or the head of the medical institution (where applicable) is responsible for study intervention accountability, reconciliation, and record maintenance (ie, receipt, reconciliation, and final disposition records).

The investigator, a member of the study site staff, or a hospital pharmacist must maintain an adequate record of the receipt and distribution of all study intervention using the Drug Accountability Form. These forms must be available for inspection at any time.

Further guidance and information for the final disposition of unused study interventions are provided in a separate document.

6.3 Measures to Minimize Bias: Randomization

All participants will be centrally assigned to randomized study intervention using an interactive web response system (IWRS). Before the study is initiated, the log-in information and directions for the IWRS will be provided to each study site.

Study intervention will be dispensed at the study visits as summarized in the Section 1.3.

Returned study intervention should not be redispensed to the participants.

If the IWRS system is unavailable, contact the medical monitor in charge of the site to solve the problem.

6.3.1 Stratified block randomization

The randomization code will be set so that the test group and control group can be assigned in a 1:1 ratio by the stratified block randomization method for each institution and using statin administration history as a stratification factor.

Inclusion criterion No. 3 is the stratification factor, and the classification is as follows:

(a) patients who failed to achieve their target LDL-C goals with low and/or moderate intensity statin mono therapy for ≥ 4 weeks

(b) patients who are statin-naïve or have not been on a stable (unchanged) statin regimen for at least 4 weeks prior to enrollment

However, in the case of (b) patients, less than 40% of each group should be recruited.

6.4 Study Intervention Compliance

The prescribed dosage and regimen of administration may not be changed. Any departures from the intended regimen must be recorded in the electronic case report form (eCRF).

Participants exhibiting poor compliance as assessed by tablet counts should be counseled on the importance of good compliance to the study dosing regimen.

Noncompliance is defined as taking less than 80% or more than 120% of study intervention during any evaluation period (visit to visit).

When participants self-administer study interventions at home, compliance with study intervention will be assessed at each visit. Compliance will be assessed by direct questioning and counting returned tablets during the study site visits and documented in the source documents and relevant form. Deviation(s) from the prescribed dosage regimen should be recorded.

A record of the quantity of study interventions dispensed to and administered by each participant must be maintained and reconciled with study intervention and compliance records. Intervention start and stop dates, including dates for intervention delays and/or dose reductions will also be recorded.

6.5 Continued Access to Study Intervention after the End of the Study

The Sponsor will not provide any additional care to participants after they leave the study.

6.6 Treatment of Overdose

In the event of an overdose, the investigator should:

- Contact the medical monitor immediately (see Section 8.4.7).
- Evaluate the participant to determine, in consultation with the medical monitor, whether study intervention should be interrupted or whether the dose should be reduced.
- Closely monitor the participant for any AE/serious adverse event (SAE) and laboratory abnormalities until end of study.
- Document the quantity of the excess dose as well as the duration of the overdose.

6.7 Concomitant Therapy

The Investigator must instruct the participant to notify the study site about any new medications he/she takes after signing the study informed consent. All medications, procedures, and significant non-drug therapies (including physical therapy and blood transfusions) administered after the participant was enrolled into the study must be recorded on the appropriate eCRFs.

Any therapy that the participant is receiving at the time of enrollment or receives during the study must be recorded along with:

- Concomitant therapy name
- Reason for use
- Period including start and end dates

In particular, in the case of medication, the following items are also collected:

- Route of administration
- Dosage information including dose and frequency

Prior medication up to 1 month prior to enrollment is also collected.

The following drugs are not allowed to be administered during the clinical trial period. However, partial permission is possible at the discretion of the investigator.

1. Lipid modulating agents other than IMP.
 - statin, fibric acid derivatives, ezetimibe, bile acid sequestrants, PCSK9 inhibitor, nicotinic acid (niacin)
 - alipogene tiparvovec, bempedoic acid, dextrothyroxine, inclisiran, lomitapide, magnesium pyridoxal 5-phosphate glutamate, meglitol, mipomersen, omega-3 triglycerides incl. other esters and acids, policosanol, probucol, tiadenol
2. Other drugs or foods that may affect blood lipids.
 - systemic steroids, lipolytic enzyme inhibitors (e.g., orlistat), hormone replacement therapy, thyroid therapy (e.g., levothyroxine, benzylthiouracil), fish oil, fiber-based laxatives, cholestine, phytosterol margarines, grapefruit.
3. Drugs with known drug interactions with IMP according to label.
 - cyclosporine, HIV protease inhibitors, hepatitis C protease inhibitors, gemfibrozil, fusidic acid.
4. Drugs or foods described in the label precautions.

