For participants whose LDL-C value has reached the target (LDL-C < 55 mg/dL) according to the lipid indicator test at Visit 3, they will continue treatment with the same dose for 6 weeks. If the LDL-C level has not reached target, the dose of atorvastatin should be increased to ezetimibe/atorvastatin 10/80 mg or atorvastatin 80 mg according to the group assigned. In principle, a morning visit is recommended so that the laboratory test results can be checked and the IMP can be prescribed and taken on the same day. However, if the test results are not confirmed on the same day and a participant has enough IMP to take until the next visit, IMP compliance is checked, and the same dose of IMP (ezetimibe/atorvastatin 10/40mg or atorvastatin 40mg) is continued. An additional visit is made within 1 week to return the remaining IMP and receive new IMP. If the test results are not confirmed on the same day and a participant does not have remaining IMP, the investigator prescribes the same dose of IMP (ezetimibe/atorvastatin 10/40mg or atorvastatin 40mg) that the participant was taking previously, and an additional visit is made within 1 week to receive new IMP. Visit 4 is the end of study visit, and tests for effectiveness and safety are conducted.

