6.1 Study Interventions Administered

Details of the treatments administered in this study are presented in Table 6–1 and Table 6–2.

Table 6–1 Study Interventions Administered

Intervention Label	Ezetimibe/Atorvastatin	Atorvastatin
Intervention Name	Atozet	Lipitor
Type	Drug	Drug
Dose Formulation	Tablet	Tablet
Unit Dose Strength(s)	10/40 mg 10/80 mg	40 mg 80 mg
Dosage Level(s)	QD	QD
Route of Administration	Oral	Oral
Use	Experimental	Active comparator
IMP and NIMP/AMP.	IMP	IMP
Sourcing	Provided centrally by the Sponsor.	Provided centrally by the Sponsor.
Packaging and Labeling Do not include a sample of the label text or details of pack design in the protocol.	Study intervention will be provided in bag. Each bag will be labeled as required per country requirement.	Study intervention will be provided in bag. Each bag will be labeled as required per country requirement.

Abbreviations: QD = once a day; IMP = investigational medical product

Table 6–2 Study Arms

Arm Title	Eze/Ato	Ato
Arm Type	Experimental	Active comparator
Arm Description	Participants will receive ezetimibe/atorvastatin 10/40 mg QD from Visit 2 (Day 1) to Visit 3 (Week 6). If the LDL-C target is reached (LDL-C < 55 mg/dL) at Visit 3, maintain the dose to Visit 4 (Week 12). If the LDL-C target level is not reached at Visit 3, dose is increased to ezetimibe/atorvastatin 10/80 mg QD from Visit 3 to Visit 4.	Participants will receive atorvastatin 40 mg QD from Visit 2 (Day 1) to Visit 3 (Week 6). If the LDL-C target is reached (LDL-C < 55 mg/dL) at Visit 3, maintain the dose to Visit 4 (Week 12). If the LDL-C target is not reached on at Visit 3, dose is increased to atorvastatin 80 mg QD from Visit 3 to Visit 4.

Associated Intervention Labels	Ezetimibe/Atorvastatin	Atorvastatin
--------------------------------	------------------------	--------------

Abbreviations: QD = once a day

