7.1 Discontinuation of Study Intervention

It may be necessary for a participant to permanently discontinue study intervention. If study intervention is permanently discontinued, the participant will remain in the study to be evaluated for lipid profile. See the SoA in Section 1.3 for data to be collected at the time of discontinuation of study intervention and follow-up and for any further evaluations that need to be completed.

The following criteria should be considered for discontinuation:

- Protocol deviation
- Lost to follow-up
- AST or ALT level $> 3 \times \text{ULN}$ for 2 consecutive times
- CK $> 10 \times \text{ULN}$ for 2 consecutive times
- Pregnancy
- Termination of the study by the investigator or Sponsor
- Difficult to continue the study according to the judgment of the investigator
- Adverse event
- Withdrew informed consent

If a participant who does not meet enrollment criteria is inadvertently enrolled, that participant must be discontinued from study intervention and the Sponsor or designee, must be contacted. An exception may be granted in rare circumstances for which there is a compelling safety reason to allow the participant to continue. In these rare cases, the investigator must obtain documented approval from the Sponsor or designee, to allow the participant to continue in the study.

Participants who discontinue study intervention will not be replaced.

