8.0 STUDY ASSESSMENTS AND PROCEDURES

Study procedures and their timing are summarized in the SoA (Section 1.3). Protocol waivers or exemptions are not allowed.

Immediate safety concerns should be discussed with the Sponsor immediately upon occurrence or awareness to determine if the participant should continue or discontinue study intervention.

Adherence to the study design requirements, including those specified in the SoA (Section 1.3), is essential and required for study conduct.

All screening evaluations must be completed and reviewed to confirm that potential participants meet all eligibility criteria. The investigator will maintain a screening log to record details of all participants screened and to confirm eligibility or record reasons for screening failure, as applicable.

Procedures conducted as part of the participant's routine clinical management (e.g., blood count) and obtained before signing of the informed consent form (ICF) may be utilized for screening or baseline purposes provided the procedures met the protocol-specified criteria and were performed within the timeframe defined in the SoA (Section 1.3).

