6.2 Per Protocol Set [PPS]

The per-protocol set (PPS) is a subset of the FAS who completed the 6-week follow-up observation with no major protocol deviations. Possible reasons excluded from PPS including major protocol violations are listed as follow:

- Violation of inclusion or exclusion criteria
- Randomization error
- No 6-week LDL-C assessment
- IP noncompliance (less than 80% or more than 120% of study intervention)
- Administration of prohibited concomitant medications
- Study discontinuation before 6-week
- Other major protocol deviations

The efficacy analysis based on the PPS will be considered supportive.

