	No baseline LDL-C assessment	00 (00.00)	00 (00.00)
	No on-treatment LDL-C assessment	00 (00.00)	00 (00.00)
Per Protocol Analysis Set			
Yes	00 (00.00)	00 (00.00)	00 (00.00)
No	00 (00.00)	00 (00.00)	00 (00.00)
	Violation of inclusion/exclusion criteria	00 (00.00)	00 (00.00)
	Randomization error	00 (00.00)	00 (00.00)
	No 6-week LDL-C assessment	00 (00.00)	00 (00.00)
	IP noncompliance	00 (00.00)	00 (00.00)
	Administration of prohibited concomitant medications	00 (00.00)	00 (00.00)
	Study discontinuation before 6-week	00 (00.00)	00 (00.00)
	Other	00 (00.00)	00 (00.00)

Deviations categories are not mutually exclusive. LDL-C: low-density lipoprotein cholesterol.

N = the number of randomized patients; n = the number of patients in each category.

Percentage (%) = 100 * (n / N).

Table 6. Individual Listing of the Patients Excluded from Each of the Analysis Set (Randomized Patients)

Patient number	Institution name	Treatment group	Sex	Age	Date of informed consent	Status of study completion	Analysis set excluded	Reasons for exclusion
000	000	000	000	000	000	000	000	000

Table 7. Major Protocol Deviations by Deviation Category (FAS)

Document: Document path and title

Template No.: CCI [REDACTED]

Reference: CCI [REDACTED]

Effective Date: 15Oct2021

	Eze/Ato (N=00) n(%)	Ato (N=00) n(%)	Total (N=00) n(%)
Any Major Protocol Deviation	00 (00.00)	00 (00.00)	00 (00.00)
Violation of inclusion/exclusion criteria	00 (00.00)	00 (00.00)	00 (00.00)
Randomization error	00 (00.00)	00 (00.00)	00 (00.00)
No 6-week LDL-C assessment	00 (00.00)	00 (00.00)	00 (00.00)
IP noncompliance	00 (00.00)	00 (00.00)	00 (00.00)
Administration of prohibited concomitant medications	00 (00.00)	00 (00.00)	00 (00.00)
Other	00 (00.00)	00 (00.00)	00 (00.00)

LDL-C: low-density lipoprotein cholesterol.

N = the number of randomized patients; n = the number of patients in each category.

Percentage (%) = 100 * (n / N).

Table 8. Individual Listing of the Patients with Major Protocol Deviations (Randomized Patients)

Patient number	Institution name	Treatment group	Sex	Age	Date of informed consent	Status of study completion	Protocol deviation category
000	000	000	000	000	000	000	000

Table 9. Demographic and Other Baseline Characteristics (FAS)

Item	Statistics	Eze/Ato (N=00)	Ato (N=00)	Total (N=00)
Age (years)				
	Nx	00	00	00
	Mean \pm SD	00.00 \pm 00.00	00.00 \pm 00.00	00.00 \pm 00.00
	Median	00.00	00.00	00.00
	Q1, Q3	00.00, 00.00	00.00, 00.00	00.00, 00.00

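### Protocol 6.7 lets investigators permit any listed drug, including ezetimibe and other lipid-lowering agents, to participants still on study drug in an open-label trial (minor)

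*Protocol*

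**What the plan says.** Protocol 6.7 prohibits four numbered lists of drugs or foods during the trial. Between the prohibition and the lists it says "However, partial permission is possible at the discretion of the investigator". List 1 covers lipid-modulating agents other than study drug and begins with "statin, fibric acid derivatives, ezetimibe, bile acid sequestrants, PCSK9 inhibitor, nicotinic acid (niacin"; a second line adds others such as bempedoic acid and inclisiran. All concomitant medication is recorded with reason, dates, dose and frequency.

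Other text that bears on the point:

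- Protocol 6.1: study tablets in both arms are "Provided centrally by the Sponsor".
- Protocol 4.1: the trial is open-label. The planned Visit 3 step, taken within the assigned arm, is: "If the LDL-C level has not reached target, the dose of atorvastatin should be increased to ezetimibe/atorvastatin 10/80 mg or atorvastatin 80 mg".
- Protocol 7.1: "If study intervention is permanently discontinued, the participant will remain in the study to be evaluated for lipid profile".
- Protocol 8.0: "Protocol waivers or exemptions are not allowed".
- SAP 6.1: the FAS analyses patients as randomized, whatever they actually took.
- SAP 6.2: the reasons for exclusion from the PPS include "Administration of prohibited concomitant medications". The PPS is supportive.
- SAP 8.2: an inferential conclusion is drawn for the primary endpoint only.

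**The concern.** Both arms follow the same atorvastatin schedule, so ezetimibe is the only planned difference between them. A rule that lets an investigator who knows the allocation add ezetimibe to the control arm permits contamination of exactly that difference. Because study tablets are supplied centrally, the opening concerns a non-study prescription of ezetimibe, or of another list 1 drug, to someone still taking study drug. The background in Protocol 2.0 supplies a motive: it says ezetimibe should be added when the goal is missed on the maximum tolerable statin dose.

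The effect depends on the drug and the arm. Ezetimibe in controls pulls the difference towards zero. A PCSK9 inhibitor or another list 1 agent in the Eze/Ato arm pushes it away from zero.

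The supportive analysis has a related gap. SAP 6.2 does not say whether a drug that the investigator has permitted still counts as prohibited, so PPS membership for such a patient is undefined.

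**Working it through.** **Does other text close the opening?**

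- The waiver ban in Protocol 8.0 does not define partial permission, and use allowed by an exception written into 6.7 need not be a waiver.
- The waiver ban in Protocol 5.0 concerns recruitment and enrolment criteria.
- Protocol 6.4 forbids changes to the study-drug regimen; it does not address added drugs.
- Where the protocol wants sponsor or monitor involvement it says so: rescreening (5.4), overdose (6.6), and ineligible participants who continue (7.1). Section 6.7 has no such requirement.

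The opening therefore stands on the text.

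**When would it be used?** The Schedule of Activities has no lipid test between Visit 2 and Visit 3, so no scheduled result prompts added therapy before the Week 6 sample. Protocol 10.2 allows additional tests at any time, so earlier use is not ruled out. After Visit 3 the result is known, but the planned step to 80 mg reduces the motive.

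**Reproducing the plan's figure.** Inputs from Protocol 9.5: difference 10 points, SD 19, two-sided alpha 0.05, power 0.80, 1:1 allocation.

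n = 2 × (1.96 + 0.842)² × 19² / 10² = 56.69, so 57 per group; 56.69 / 0.9 = 62.99, so 63 randomized per group. Both agree with the protocol.

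**Precision with 57 per group, unadjusted.** SE = 19 × √(2/57) = 3.559. With t(112 df, 0.975) = 1.981, the 95% CI half-width is 7.05.

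**Dilution from ezetimibe in controls.** Assume k of 57 controls take it and have its full 10-point effect at the sample. The expected difference shrinks by 10 × k/57. Power is two-sided at 0.05 from the noncentral t with 112 df.

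| k | Shift (points) | Expected difference | Shift as % of half-width | Power if before Week 6 |
|---|---|---|---|---|
| 0 | 0 | -10.0 | 0 | 79.5% |
| 1 | 0.175 | -9.8 | 2.5% | 78.1% |
| 3 | 0.526 | -9.5 | 7.5% | 75.1% |
| 6 | 1.053 | -8.9 | 14.9% | 70.3% |

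The normal approximation gives 80.2% at k = 0, which matches the planned 80%; the noncentral t is slightly lower. At Week 12 only the shift applies, and only if the Week 6 planning values hold there. The values of k are assumptions. The documents give no effect size for other list 1 drugs, so widening from their use in the Eze/Ato arm cannot be quantified.

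**The case against.** Five points can fairly be made on the other side.

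1. **Use would be visible.** SAP 13 and Table 14 tabulate concomitant medication by name and arm in the FAS, and Tables 5 and 7 count prohibited-medication cases. This stands in part. Table 14 gives no timing against the Week 6 or Week 12 samples, and because it counts any drug stopped on or after first dose, it mixes background statin that ended on Day 1 with later additions.

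2. **The primary analysis already has a rule, and the exposure is small.** The FAS keeps everyone as randomized, one contaminated control moves the estimate by 2.5% of the CI half-width, and the 70.3% figure needs six controls with full ezetimibe effect at Week 6 without a scheduled lipid result to prompt it. This stands and limits the point to minor.

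3. **Discretion with full recording is a legitimate choice in a Phase 4 effectiveness trial.** For lists 2 to 4 that is reasonable. For list 1 it reaches the randomized contrast itself, and participants already have the 80 mg step.

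4. **The sponsor may have meant something narrower by partial permission.** That is possible, but the text does not say so.

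5. **The PPS gap rests on little.** A reader might infer from the heading "Table 7. Major Protocol Deviations by Deviation Category (FAS)" that permitted use is not a deviation and so stays in the PPS. The heading is weak evidence: SAP 6.2 describes exclusion reasons that include, but are not confined to, major violations, and Table 5 lists prohibited medication directly as a reason. What remains is that no text settles the matter either way.

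**Conclusion.** The point holds as a minor one. Protocol 6.7 as written allows list 1 drugs, including ezetimibe, to be given to participants on study drug in either arm, without sponsor approval or a time limit. The likely consequence is some contamination of the Week 12 endpoints, on which the SAP draws no inferential conclusion. Loss of power for the primary test is possible but probably at the small end of the illustrated range. That range rests on assumed counts, full ezetimibe effect by the sample, and the plan's own difference and SD.

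Two stronger readings are not supported. A reader might infer that contamination can only make the trial conservative and so could never help a false superiority claim. That is true of ezetimibe given to controls, but not of other list 1 drugs given in the Eze/Ato arm. A reader might also infer that the primary result is compromised. The documents give no rate of such use, and the timing of lipid tests and the 80 mg step both argue against frequent use before Week 6.

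**What to change.** **Protocol 6.7.** State that the discretion does not apply to list 1 agents while the participant is taking study drug, up to the Week 12 sample. Participants who have permanently stopped study drug but remain in follow-up may receive lipid therapy as clinically needed, with dates recorded. Treat fish oil (now list 2, while omega-3 products are in list 1) and gemfibrozil (now list 3, but a fibric acid derivative and so also list 1) as list 1, so that no product falls under two rules.

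**SAP 6.2.** State that any list 1 use from the day after first dose to the Week 6 LDL-C sample excludes from the PPS, whether or not it was permitted. Starting on the day after first dose avoids excluding stratum (a) patients whose background statin ended on Day 1. No PPS rule based on permission records is proposed for lists 2 to 4, because the documents name no data field for such permission.

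**Reporting.** To supplement Table 14, give by arm the number of patients with list 1 use before the Week 6 sample and before the Week 12 sample, split into use on and off study drug. Leave the FAS unchanged.

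**Cost.** A short protocol amendment with IRB/IEC approval, a few SAP lines, and counts from medication dates already collected. Investigators lose discretion over list 1 for participants on study drug, and the PPS may become slightly smaller. If enrolment is over, only the SAP lines and the counts apply.
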